9. SAFETY REPORTING

Participants in the shorter treatment duration arm may experience an increase in incidence of VAP relapse. Participating in the study will not delay the participants from receiving antibiotic treatment for recurrent VAPs. Decision to treat these participants for VAP recurrence will be made by the primary physicians.

For outcome measurement purposes, opinion from 2 respiratory experts blinded to the randomisation will be sought to diagnose recurrences according to the above-described clinical and radiological criteria of VAP. Interim analysis will be done to ensure that participants in the shorter treatment duration arm are not experiencing a significant increase in incidence of ventilator-associated pneumonia relapse.

9.1. Definition of Serious Adverse Events

A serious adverse event is any untoward medical occurrence that:

- results in death
- is life-threatening
- requires inpatient hospitalisation or prolongation of existing hospitalisation
- results in persistent or significant disability/incapacity

Other 'important medical events' may also be considered serious if they jeopardise the participant or require an intervention to prevent one of the above consequences.

NOTE: The term "life-threatening" in the definition of "serious" refers to an event in which the participant was at risk of death at the time of the event; it does not refer to an event which hypothetically might have caused death if it were more severe.

9.2. Reporting Procedures for Serious Adverse Events

Given that VAP in ICU cohorts is associated with high mortality of 13.6–42.8% [41] and high recurrence rate previously shown in Southeast Asia, we would expect 55%-60% of our estimated sample size of 460 patients to fulfil the above definition of SAE. This constitutes up to 276 (138 in each arm) participants that would require SAE reporting.

As these events are very frequent and expected outcomes from ICU cohorts of patients, local Investigators will report mortalities and VAP recurrences that were 'definitely related' (definitely resulted from shortening antibiotic therapy duration), 'probably related' (some evidence that the event was resulted from shortening antibiotic therapy duration), 'possibly related' (little evidence that the event was resulted from shortening antibiotic therapy duration), and 'not related' (no evidence that the event was resulted from shortening antibiotic therapy duration) to CI on a monthly basis in the form of collated SAE reports. CI will, in turn, present these collated SAE reports to a nominated member of Data and Safety Monitoring Committee (DSMC) on a monthly basis.

Local investigator will present these SAE to the relevant local authorities according to local reporting requirements and timelines.

To address the main risk of our study, which is that the participants in the intervention arm (short duration) may have higher recurrence and mortality rates, we have planned for four interim analysis for safety monitoring by the Data and Safety Monitoring Committee (DSMC).

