7.4. Randomisation, blinding and unblinding

Randomisation will be done via stratified block randomisation by the study sites to ensure participants with similar characteristics such as gender and age are distributed equally in the intervention and control groups. Randomisation will be done with a computer programme with a seed to allow reproducibility. Randomisation will be done with a 1:1 ratio. To prevent predictability of the random sequence, generation of the randomisation sequence is performed by an independent statistician and details of the randomisation generation is unavailable to all investigators. Randomisation will be allocated using sequentially numbered opaque envelopes. Fitness criteria for randomisation (section 8) must be met prior to randomisation.

Patients will be blinded to the study, as they will not be informed of the treatment duration and likely to be sedated and unaware of the treatment regimens. Investigators will be blinded during the assessment of the participants for clinical stability based on the above-described criteria to minimise observer bias. Once conditions for stopping antibiotics are satisfied, the investigator will be unblinded and contact the primary physicians to stop antibiotics. The physicians will remain blinded until they are informed that the participant is suitable to stop antibiotics. Independent assessors, who are assigned to determine pneumonia recurrences, will be blinded from the randomisation arms. This will be achieved by blinding all study details, including randomisation arms, for participants with potential recurrences from these independent assessors.

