Persistent VAP or treatment failure is defined as the lack of improvement of hemodynamic stability or ventilation requirements without an alternative cause other than the same episode of VAP. These patients will be continued to be monitored for the above-described “fitness criteria” and antibiotics should be stopped when they eventually meet the criteria. Recurrent VAP is defined as an additional episode of VAP satisfying the CDC clinical and radiological criteria of VAP [29] following commencement of the primary VAP treatment within 60(+5) days of enrolment. Opinion from 2 respiratory experts blinded to the randomisation will be sought to diagnose persistence and recurrences. Patients who are diagnosed with an alternative source of infection or a complication from VAP such as lung abscess or empyema that warrant a duration of antibiotics longer than 7 days prior to the last day of assigned duration of antibiotics are not considered treatment failures. These patients will not meet fitness criteria for randomisation and be discontinued from the study and subsequent analysis (see section 7.8). In cases where patients randomised to short duration and satisfy the above-described “stop criteria” but did not have their antibiotics stopped by day 7, they are considered protocol deviations. They will be analysed with intention to treat analysis.

Duration of antibiotics in control group will be at least 8 days with the exact duration decided by the managing physicians.

Adverse events will be recorded throughout the study period, including *C. difficile* infection, acute kidney injury, hepatitis, drug allergies, haematological and other complications.

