4. DATA SAFETY MONITORING COMMITTEE AND INTERIM ANALYSES

The data safety and monitoring committee (DSMB) consists of members independent from the study investigator team. The DSMB will review the analysis plan, interim analyses results, and their approval will be required before protocol and analysis plan amendments. The DSMB will receive reports regarding severe adverse events on a monthly basis, and will review the final study report. The DSMB will be empowered to advise stopping or suspending the trial, independent of the study investigators.

DSMB meetings should be held with every interim analysis and extra meetings may be convened at the request of the investigators, sponsor, or DSMB members to discuss emerging data that is a cause for concern. A full interim analysis including all available data from all sites will be reviewed by the DSMB after approximately 25% (125) participants from sites have been recruited and completed their follow-up to review the safety and ethics of the REGARD-VAP trial. Hence there will be four interim analyses will be performed on the primary endpoint.

A trial steering committee will also be constituted and will decide on the continuation of the trial and will report to the central ethics committee. The trial will be terminated if superiority of either short or long treatment durations is shown. We will use the group sequential design adopting the boundaries proposed by Fleming- Harrington- O'Brien ($R=0.8$)⁵ to terminate the trial prematurely once the Z value exceeds the defined boundaries for superiority.

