8.3. Adverse Events and Complications

Episodes of antibiotic-related diarrhoea, allergy reactions and other side effects, readmissions will be summarised overall and by treatment arm (frequency and percentages). Participants will be categorised as either having or not having experienced adverse events. Using this as a binary outcome variable, the analysis described in section 7.2 will be repeated.

A breakdown of serious adverse events (SAE) will also be presented in this section. SAEs in REGARD-VAP trial include deaths and pneumonia recurrences, which already contribute to the primary outcome. In a detailed breakdown of these SAEs, the number of participants with at least one recorded SAE, as well as the number of SAE reported per participant will be included. In addition, summaries will include the timing of the report from randomisation and whether complications were expected and / or thought to be related to the randomisation, and the outcome of any SAEs will be summarised.

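### Protocol 9.2 names only deaths and VAP recurrences for the monthly SAE report and grades causality only against shortened treatment, which does not match Protocol 9.1 or SAP sections 4 and 8.3

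*Protocol*

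**What the plan says.** **Definition.** Protocol 9.1 uses a general SAE definition. Besides death it covers life-threatening events, any event that "requires inpatient hospitalisation or prolongation of existing hospitalisation", lasting disability, and other important medical events.

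**Reporting step.** Protocol 9.2 argues that such events will be common: "we would expect 55%-60% of our estimated sample size of 460 patients to fulfil the above definition of SAE". It then sets the procedure: "local Investigators will report mortalities and VAP recurrences that were 'definitely related' (definitely resulted from shortening antibiotic therapy duration". The 'probably', 'possibly' and 'not related' grades follow, each also defined by whether the event came from shortening therapy. Sites send these reports to the chief investigator, who passes them monthly to a nominated member of the monitoring committee.

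**Antibiotic harms.** Protocol section 8 has adverse events recorded throughout. It names C. difficile infection and "acute kidney injury, hepatitis, drug allergies, haematological and other complications". Section 9 does not say what a site does when one of these is serious.

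**SAP.** Section 4 is wider: "The DSMB will receive reports regarding severe adverse events on a monthly basis". Section 8.3 says "SAEs in REGARD-VAP trial include deaths and pneumonia recurrences, which already contribute to the primary outcome" and plans to summarise whether complications were thought related to randomisation. It gives no scale for that judgement.

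**The concern.** Protocol 9.2 is the only text that tells a site what to send upward, and it lists two event types. A site that follows it exactly is not told to include a serious allergic reaction, kidney injury or C. difficile infection unless the participant dies or has a recurrence. The committee's monthly report would then be narrower than SAP section 4 implies.

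The causality scale has a separate problem. It asks one question, whether shortening the course caused the event. That addresses the main feared risk of the short arm. It has no counterpart for harm from longer exposure, although adverse events, resistance acquisition and total antibiotic exposure are all secondary endpoints. At stake are the completeness of routine safety reporting and the meaning of one descriptive summary in the final report.

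**Working it through.** **Step 1: reproduce the plan's figure.** Inputs: 460 participants and 55% to 60% with an SAE (Protocol 9.2); equal allocation (Protocol 7.4: "Randomisation will be done with a 1:1 ratio").

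- Upper end: 460 × 0.60 = 276. Per arm: 276 / 2 = 138.
- Lower end: 460 × 0.55 = 253.

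The protocol states "This constitutes up to 276 (138 in each arm) participants that would require SAE reporting", so the figure reproduces exactly.

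**Step 2: what the figure counts.** Protocol 9.2 derives it from VAP mortality and recurrence. Its lower end, 55%, equals the rate assumed for the death-or-recurrence composite in the protocol's section on the number of participants. The remaining 276 − 253 = 23 participants are not explained. No separate allowance for other serious events is stated, so the projection appears to rest on primary-endpoint events.

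**Step 3: set the scopes side by side.**

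| Place | Events covered | What happens to them |
|---|---|---|
| Protocol 9.1 | All events meeting a seriousness criterion | Definition only |
| Protocol 9.2 | Deaths and VAP recurrences | Monthly, site to chief investigator to committee member |
| Protocol 8 | Adverse events, including named antibiotic harms | Recorded; no escalation step |
| SAP 4 | Severe adverse events, not listed | Monthly to the committee |
| SAP 8.3 | SAEs, said to include deaths and recurrences | Final report |

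Protocol 9.2 is narrower than both 9.1 and SAP 4. SAP 4 says what the committee receives, not what sites submit, and severe is not the same as serious.

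**Step 4: apply the scale by arm.** In the short arm, all four grades can be used for harm attributed to stopping early, but none fits harm from the antibiotics themselves. In the long arm treatment was not shortened, so the only coherent answer is 'not related', whatever the cause. At the protocol's maximum, 138 of 276 projected participants with an SAE (138 / 276 = 50%) are in that position.

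**Step 5: follow it into the report.** SAP 8.3 needs a relatedness judgement, and Protocol 9.2 holds the only relatedness scale in either document. If those grades are used, entries above 'not related' can arise only in the short arm.

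**What cannot be computed.** Neither document gives a rate of serious antibiotic harm, so the number of events without a named reporting step cannot be estimated from them.

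**The case against.** The strongest reply is that oversight does not rest on Protocol 9.2 alone. SAP 4 promises monthly reports without limiting them to two event types, allows extra meetings, and describes interim review of all available data. Protocol 10.3 gives the committee unblinded access to all data. A reader might infer that serious antibiotic harms never reach the committee; these passages do not support that.

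Nor are the harms of longer treatment left unmeasured. Adverse events are recorded weekly (SAP 2.7), are a secondary endpoint (SAP 2.6) and are analysed by arm (SAP 8.3). A fatal antibiotic harm would be reported under 9.2 as a death.

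A reader might also infer that the SAE comparison between arms is distorted. It is not: 9.2 has deaths and recurrences reported at every grade, including 'not related', so grading removes none of them. The number of participants with an SAE, SAEs per participant, timing and outcome do not depend on relatedness. SAP 8.3 words relatedness neutrally and does not say that it reuses the 9.2 grades.

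Finally, collating frequent, expected events is reasonable in ventilated patients, and full reporting under 9.1 could add noticeable work.

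All of this stands and limits the point. It does not supply the missing site instruction. The interim analyses are specified on the primary endpoint, with no planned comparison of other SAEs. It also leaves the one-way scale as it is. That deaths and recurrences are frequent justifies collating them; it does not explain silence on other serious events.

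**Conclusion.** The point holds as a mismatch between sections together with a one-way causality scale. Protocol 9.2 names fewer events than 9.1 defines or SAP 4 promises, and serious antibiotic harms other than death or recurrence have no explicit site-level reporting step. On the scale as worded, none of the long-arm SAEs (138 at the protocol's own maximum) could be graded above 'not related', and no grade in either arm captures harm from antibiotic exposure.

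This rests on three assumptions. The first is a literal reading of the grades: that long-arm events can only be 'not related' is an inference, not a stated rule. The second is that sites report what 9.2 lists and no more. The third concerns only the report: the relatedness summary is one-sided if SAP 8.3 draws on the 9.2 grades. The 138 projects participants with an SAE on a death-and-recurrence basis and says nothing about how often antibiotic harms occur.

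The scale does not change SAE counts by arm, and neither issue changes the primary endpoint or its estimate. This is a worthwhile correction to safety reporting and does not threaten the trial's main conclusion.

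**What to change.** - **Protocol 9.2, scope.** Reconcile with 9.1 and SAP 4. Keep deaths and recurrences as collated expected events. State that other events meeting 9.1, at least the antibiotic harms named in Protocol section 8, go into the same monthly report to the committee.
- **Protocol 9.2, scale.** Replace the four grades with relatedness to the allocated antibiotic duration or to antibiotic exposure, applied identically in both arms.
- **SAP 4.** Say whether severe means serious as defined in 9.1.
- **SAP 8.3.** Tabulate all events qualifying under 9.1 by arm, and name the relatedness scale used. Omit grades collected on the one-way scale, or caveat them plainly.

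The cost is wording in both documents and some additional SAE forms. How many depends on how much of 9.1 is brought in, and limiting the addition to the named antibiotic harms keeps it small because those events are already recorded. SAP 2.2 gives 16 December 2022 as the end of recruitment and 14 February 2023 as the end of follow-up. After those dates a change to 9.2 cannot alter what sites have already sent, but the SAP 8.3 change can still be made from recorded adverse events. A monthly by-arm summary from the statistician to the committee would be an optional extra.

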10. STATISTICS AND ANALYSIS

10.1. Description of Statistical Methods for Primary and Secondary Outcomes

Descriptive statistics will include frequency tables for categorical data, means (SDs), or medians (interquartile ranges) depending on the distribution of the data. Categorical variables will be compared with χ^2 and Fisher exact tests as appropriate and continuous variables with unpaired, 2-tailed t tests or nonparametric Wilcoxon rank sum tests as appropriate.

The primary and secondary outcomes of the study populations will be analyzed using both unadjusted and adjusted methods in both the per-protocol and intention-to-treat populations. Adjustment will be done with inverse probability weighting, using baseline patient characteristics (study site, age, gender, comorbidities, residence prior to admission, type of ICU admitted to, SOFA score, VAP infection with CRE, maximum heart rate and minimum mean arterial blood pressure on randomisation day, duration of intubation prior to developing VAP, reason for intubation, number of days from first respiratory symptom onset to first day of appropriate antibiotics) as independent variables.

Subgroup analysis will be performed using the primary outcome as the dependent variable amongst patients with VAP caused by Gram-negative non-fermenters and carbapenem-resistant bacilli. VAPs caused by Gram-negative non-fermenters have been previously shown to be associated increased recurrence [10,11]. VAPs caused by carbapenem-resistant bacilli have no standardised treatment. This will be exploratory as the sample sizes for each of this groups will not reach adequate power.

This is a non-inferiority trial with a hierarchical noninferiority–superiority hypothesis. The first analysis to be conducted will be for determination of non-inferiority. Only if non-inferiority is established by this primary analysis, a second analysis for superiority will be conducted using closed testing methods without requiring adjustment of the significance level for multiple comparisons. [39] The trial estimates for the primary outcome will be calculated with the absolute risk difference (proportion of participants with the primary outcome in the short arm minus that in the long arm). Hence, non-inferiority will be concluded if the upper boundaries of the one-sided 95% confidence intervals from both unadjusted and adjusted analyses are below the non-inferiority margin. The purpose of using both adjusted analyses on the intention-to-treat and per-protocol populations to determine non-inferiority is to minimise the inflation of type 1 error associated with non-adherence in non-inferiority trials. [40] Superiority will be declared if the entire confidence intervals for all the trial estimates are above zero.

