4. OBJECTIVES AND OUTCOME MEASURES

Objectives	Outcome Measures	Timepoint(s) of evaluation of this outcome measure (if applicable)
Primary Objective To demonstrate clinical non-inferiority, followed by superiority, of a shorter antibiotic treatment duration compared to a longer duration in adult patients with VAP	Difference in the proportion of participants with the composite endpoint of death and VAP recurrence rate within 60(± 5) days of enrolment	All outcome measures will be assessed within day 60(± 5) of enrolment
Secondary Objectives To define other clinical benefits of shorter antibiotic treatment duration compared to a longer duration in adult patients with VAP	Ventilator-associated events, duration of mechanical ventilation, duration of hospitalisation, acquisition of multidrug resistant infection or colonisation during the hospitalisation, number of days of exposure to antibiotics during hospitalisation, number and types of extrapulmonary infections during hospitalisation (determined from cultures taken from sterile sites), difference in the proportion of participants with primary outcome in subgroups of patients with VAP caused by Gram-negative non-fermenters and carbapenem-resistant bacilli	All outcome measures will be assessed within day 60(± 5) of enrolment
To study the impact of various antibiotic regimen on the microbial community dynamics and diversity in the respiratory and intestinal tracts in individual patients in order to understand colonisation and transmission of MDROs, identify potentially protective components of the microbiome against MDROs	Characteristics of the microbiota will be determined by comparing alpha and beta diversity metrics between the groups of patients, alterations in the repertoire of antibiotic resistant genes, shifts in microbiota functional and metabolic capacity	Respiratory and stool samples will be collected from the study participants within 24 hours of enrolment, weekly during hospitalisation, and at day 28 (± 5) and 60(± 5) after enrolment

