10.2. Definitions of study populations

Intention-to-treat: The intention-to-treat population includes all study participants who have been randomised during the conduct of the study

Per-protocol: The per-protocol population includes all study participants who fulfill eligibility criteria specified in the inclusion/exclusion criteria (section 6.2 and 6.3), fitness criteria for randomisation (section 8) and received 7 days or less of appropriate antibiotics in the short arm, and 8 days or more of appropriate antibiotics in the long arm.

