H_1 : There is a difference in the total duration of mechanical ventilation in the short and long treatment strategy groups, i.e. $t^v_s \neq t^v_l$;

where t^v_s is the duration of mechanical ventilation in the short and t^v_l is the duration of mechanical ventilation in the long treatment strategy groups.

c) Duration of hospitalisation

Definition: Total duration of hospitalisation during the 60 days of follow-up after enrolment.

H_0 : There is no difference in the total duration of hospitalisation in the short and long treatment strategy groups, i.e. $t^h_s = t^h_l$;

H_1 : There is a difference in the total duration of hospitalisation in the short and long treatment strategy groups, i.e. $t^h_s \neq t^h_l$;

where t^h_s is the duration of mechanical ventilation in the short strategy group and t^h_l is the duration of mechanical ventilation in the long treatment strategy group.

d) Acquisition of multidrug resistant infection or colonisation during the hospitalisation

Definition: Growth of multidrug resistant bacteria⁶ from clinically indicated or screening cultures from any source during 60 days of follow-up.

H_0 : There is no difference in the proportion of participants who colonised with multidrug resistant bacteria in the short and long treatment strategy groups, i.e. $\theta^{\text{MDR}} = 0$;

H_1 : There is a difference in the proportion of participants who have ventilator-associated events in the short and long treatment strategy groups, i.e. $\theta^{\text{MDR}} \neq 0$;

where θ^{MDR} is the treatment effect difference between the proportion of participants in the short and long treatment strategy groups.

e) Total number of days of exposure to antibiotics

Definition: Total duration of antibiotic use during the 60 days of follow-up after enrolment.

H_0 : There is no difference in the total duration of antibiotic use in the short and long treatment strategy groups, i.e. $t^a_s = t^a_l$;

H_1 : There is a difference in the total duration of antibiotic use in the short and long treatment strategy groups, i.e. $t^a_s \neq t^a_l$;

where t^a_s is the duration of antibiotic use in the short and t^a_l is the duration of mechanical ventilation in the long treatment strategy groups.

f) Number and types of extrapulmonary infections during hospitalisation (determined from cultures taken from sterile sites)

Definition: Number and types of bloodstream, bone and joint, intracranial, intraabdominal infections during 60 days of follow-up.

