6. PATIENT GROUPS FOR ANALYSIS

The following patient populations will be utilised in the analysis:

Intention-to-treat (ITT)

The intention-to-treat population includes all study participants who have been randomised during the conduct of the study

Per-protocol

The per-protocol population includes all study participants who fulfill eligibility criteria specified in the inclusion/exclusion criteria, fitness criteria for randomisation and who received 7 days or fewer of appropriate antibiotics in the short arm, and 8 days or more of appropriate antibiotics in the long arm (Section 5.5).

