7. ANALYSES TO ADDRESS PRIMARY AIMS

All analyses will be formed with R⁷. All packages used in the analysis will be cited according with the corresponding version numbers. All analysis code will be published in an open access online repository with the final manuscript.

All primary and secondary outcomes of the study populations will be analysed using both unadjusted and adjusted methods in both the PP and ITT populations. The purpose of using both adjusted analyses on the intention-to-treat and per-protocol populations to determine non-inferiority is to minimise the inflation of type 1 error associated with non-adherence in non-inferiority trials⁸.

Multivariable regressions will be performed with inverse probability weighting, using baseline patient characteristics (study site, age, sex, comorbidities, residence prior to admission, type of ICU admitted to, SOFA score, VAP infection with CRE, maximum heart rate and minimum mean arterial blood pressure on randomisation day, duration of intubation prior to developing VAP, reason for intubation, number of days from first respiratory symptom onset to first day of appropriate antibiotics) as independent variables.

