8.1. Statistical Methods Used for Analysis of Secondary Outcomes

The primary analyses described in section 7.2 will be repeated for secondary outcomes, based on the ITT population. Similar analysis on the PP population will be included in the supplementary materials.

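### The supplementary per-protocol test of total antibiotic days compares groups selected on antibiotic days, so its difference arises largely by construction; test this outcome in ITT only

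*Protocol*

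**What the plan says.** Protocol 10.1 states: "The primary and secondary outcomes of the study populations will be analyzed using both unadjusted and adjusted methods in both the per-protocol", and the sentence goes on to add the ITT set, so that every outcome is analysed "in both the per-protocol and intention-to-treat populations". SAP section 7 says the same ("adjusted methods in both the PP and ITT populations"). SAP 8.1 then ranks the two for secondary outcomes. The section 7.2 analysis is repeated on the ITT population, and for PP: "Similar analysis on the PP population will be included in the supplementary materials".

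Antibiotic exposure is one of those outcomes. Protocol section 4 lists "number of days of exposure to antibiotics during hospitalisation", and SAP 2.6(e) has "Definition: Total duration of antibiotic use during the 60 days of follow-up after enrolment". SAP 8.6 gives it a Wilcoxon rank sum test and then a repeat of the section 7.2 analysis. SAP 2.6 makes secondary tests two-sided superiority tests, and SAP 7.3 sets the level at 0.05. No section exempts this outcome from the PP analysis.

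The PP population in the protocol's definitions of study populations is limited to participants who "received 7 days or less of appropriate antibiotics in the short arm, and 8 days or more of appropriate antibiotics in the long arm". SAP section 6 has the same rule and points to the adherence definition in SAP 5.5. Under 5.5, antibiotics may be restarted after the index course.

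**The concern.** Total antibiotic days is the index course plus any later courses. PP membership is decided by the index course, with opposite cut-offs in the two arms: long courses are removed from the short arm and short courses from the long arm. The comparison thus conditions on a component of what it measures. A gap appears even if randomisation has changed nothing about prescribing.

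SAP 7.2 adjusts the PP estimate by inverse probability weighting on baseline characteristics. That cannot help. Whatever the baseline profile, no short-arm PP participant has an index course above 7 days and no long-arm PP participant has one below 8, so no weighting can restore the missing part of either distribution.

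At stake is how the supplementary result is read. Reducing antibiotic consumption is a stated aim (Protocol section 3). A PP estimate and p-value beside the ITT result would look like independent confirmation, often with a larger saving, when much or all of it comes from the selection rule.

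**Working it through.** **No figure to reproduce.** The documents state no effect size, SD or power for antibiotic days. The check asks what the planned PP comparison returns under known conditions.

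**Inputs from the documents.** 230 per arm (SAP 2.2); PP cut-offs of 7 or less and 8 or more; two-sided test at 0.05; restarts allowed. The only usual-care duration given is a median of 12–13 days in Thailand (Protocol section 3).

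**Assumed inputs.** Lognormal index duration, the same in both arms, median *m* = 8, 10, 12 or 13 days and log-SD *s* = 0.3 or 0.5. Later antibiotics in 0%, 40% (mean 10 days) or 70% (mean 15 days) of participants. Days counted in full or from randomisation, because SAP 2.6(e) and 8.6 differ on the starting point. Total capped at 60 days.

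**Closed form, no later antibiotics, identical arms.** Days are whole numbers, so the cut lies at 7.5. Let z = ln(7.5/m)/s and mean μ = m·exp(s²/2).

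- Share of short arm kept: p = Φ(z)
- Mean kept in short arm: μ·Φ(z − s)/p
- Mean kept in long arm: μ·[1 − Φ(z − s)]/(1 − p)

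For m = 12, s = 0.5:

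- z = ln(0.625)/0.5 = −0.940, so p = 0.174. PP keeps 0.174 × 230 ≈ 40 short-arm and 190 long-arm participants.
- μ = 12 × exp(0.125) = 13.60, and Φ(−1.440) = 0.0749.
- Short-arm PP mean = 13.60 × 0.0749/0.1736 = 5.87 days.
- Long-arm PP mean = 13.60 × 0.9251/0.8264 = 15.22 days.
- Difference = 5.87 − 15.22 = −9.35 days, although the true difference is 0.

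Simulation of the same case also gives −9.35 days.

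**Simulation, identical arms, 400 trials per scenario, Wilcoxon at 0.05.**

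| Population | Mean difference (short − long) | Significant |
|---|---|---|
| PP, all scenarios | −3.6 to −10.2 days | 44% to 100% (90% or more in most) |
| PP, m = 12, s = 0.5 | about −9 days | 98% to 100% |
| ITT, all scenarios | −0.1 to +0.1 days | 2% to 8% |

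The Monte Carlo standard error of a 5% rate is √(0.05 × 0.95/400) = 1.1 points, so the ITT range fits a nominal 5%. The lowest PP rates come with m = 13, s = 0.3 and heavy later use, where only about 8 short-arm participants qualify for PP. Later courses add noise and so lower the rejection rate. They barely move the expected gap.

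**Simulation when the intervention works** (assumed m = 12, s = 0.4, later antibiotics in 40%; absolute differences in days).

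| Short-arm adherence | ITT | PP | PP minus ITT |
|---|---|---|---|
| 50% | 3.5 | 7.9 | 4.4 |
| 70% | 5.0 | 8.0 | 3.0 |
| 80% | 5.6 | 7.9 | 2.3 |
| 90% | 6.3 | 7.9 | 1.7 |
| 100% | 7.1 | 8.0 | 0.9 |

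The PP estimate stays at about 8 days while the ITT estimate doubles. PP hardly registers how far prescribing changed.

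**The case against.** The strongest reply is about scope. SAP 8.1 already makes ITT the main analysis for this outcome and puts PP in a supplement. SAP 5.5 reports the number of non-adherent participants with reasons and the percentage restarted in the short arm, so a reader could see how the PP set was formed. Identical prescribing in both arms is also an extreme case, since SAP 2.7 has short-arm antibiotics stopped on the day of randomisation. With good adherence the distortion is a day or two on a real effect. All of this stands and limits the importance of the point. None of it exempts total antibiotic days from a PP test that does not measure the effect of assignment.

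A reader might infer more than the documents support:

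- **That the PP result is always significant.** It is not; under the assumptions above the rate falls as low as 44%.
- **That the trial's antibiotic-saving result is invalid.** The ITT comparison is unaffected, and the primary endpoint is not at issue here.
- **That the PP estimate drives the economic case.** Protocol 10.4 uses trial data on antibiotic use without naming a population, and SAP 8.9 leaves the economics to a separate plan. Nor is antibiotic exposure called the main benefit; it is one of several secondary outcomes.
- **That hospital stay needs the same change.** A long-arm PP participant must still be on treatment at day 8, which hints at a floor on stay. But Protocol section 5 includes oral antibiotics, so treatment need not mean being an inpatient, and no effect on stay has been quantified.

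**Conclusion.** The point holds for one analysis: the two-sided test of total antibiotic days in the PP population. As written, that test selects on part of its own outcome, and baseline weighting cannot repair it. Under assumed duration distributions identical in both arms, it shows a spurious difference of roughly 4 to 10 days, significant in 44% to 100% of simulated trials, against about 0 days and about 5% in ITT. If the intervention works and adherence is high, PP overstates the ITT difference by about 1 to 2 days; at 50% adherence the excess is 4.4 days.

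The direction follows from the definitions alone. The size rests on the assumed distributions, of which only the 12–13 day median has a source in the documents. Because the analysis is supplementary and the main one is sound, this is a small correction, worth making before the PP result is reported.

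**What to change.** In Protocol 10.1 and SAP 7, 8.1 and 8.6, state that total antibiotic days is tested in the ITT population only. Suggested wording: *Total antibiotic days will be compared between arms in the ITT population only, because PP membership is defined by antibiotic duration. Any PP durations will be summarised by arm, without a test or a confidence interval for the difference.* SAP 5.5 already takes this approach to index-course duration, which it plots without statistical analysis.

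The cost is one sentence, cross-referenced in those sections, and one fewer supplementary test. No data collection, sample size or primary analysis changes.
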